2.4.3.2 Compliance

Not applicable.

2.4.4 Analyses of efficacy endpoints

2.4.4.1 Analysis of primary efficacy endpoint(s)

2.4.4.1.1 Primary efficacy analysis

First step analysis:

The statistical test for non-inferiority assessment of SAR341402 versus NovoLog/NovoRapid on the primary efficacy endpoint (change in HbA1c from baseline to Week 26 as defined in the Section 2.1.3.1) will be one-sided, with alpha level of 0.025 and using a non-inferiority margin of 0.3% HbA1c.

The primary endpoint will be analyzed in the ITT population using all post-baseline data available during the main 6-month randomized period (ITT estimand).

The analysis for change in HbA1c should account for missing data in a fashion consistent with what the measurement would have been, had it been measured. The behavior of missing data for those patients who are off-treatment may not be the same as that of observed data for those patients who are on-treatment in the same treatment arm. Therefore, it may not be appropriate to represent the missing data from patients who do not adhere to therapy by the data from those patients on the same arm who adhere to therapy.

Statistical Analysis Plan SAR314102-EFC15081 - insulin aspart 28-Feb-2018 Version number: 1

As a consequence, a multiple imputation approach will be used where missing data from patients who do not adhere to IMP will be represented by the data from those patients in the same treatment group who also do not adhere to IMP but have the measurement for the primary endpoint. Imputations will be performed with the MI procedure in SAS (Statistical Analysis System). Details of the proposed multiple imputation analysis in two parallel parts (according the status of the patients), are provided below:

Part1: Imputation for missing data in patients who prematurely discontinued IMP during the main 6-month randomized period:

Missing data in patients who prematurely discontinued IMP during the main 6-month randomized period will be imputed using a model estimated solely from data observed in other patients who discontinued IMP during the main 6-month randomized period but have the measurement for the primary endpoint at Week 26. Due to the anticipated small number of these latter patients, a basic imputation model will be built, including only the randomized treatment group as predictor. Missing data will be imputed using the regression method.

Part2: Imputation for missing data in patients who completed the main 6-month treatment period:

Missing data in patients who completed the main 6-month treatment period will be imputed separately, using a model estimated solely from data observed in other patients who completed the main 6-month treatment period and have the measurement for the primary endpoint at Week 26. Since in general, the missing pattern will not be monotone, a two-step approach will be used:

- Step 1: the Markov Chain Monte Carlo (MCMC) method will be used in conjunction with the IMPUTE=MONOTONE option to create an imputed data set with a monotone missing pattern. The imputation model will include the continuous fixed covariates of the baseline HbA1c value as well as the changes from baseline in HbA1c at Week 12 and Week 26.
- Step 2: using the monotone data set from step 1, missing data will be imputed using the regression method. The imputation model will include the fixed categorical effects of the treatment group, the randomization strata of geographical region and type of diabetes (Europe T1DM, US T1DM, US T2DM, Japan T1DM) and prior use of NovoLog/NovoRapid (Yes, No), as well as the continuous fixed covariates of the baseline HbA1c value and the changes from baseline in HbA1c at Week 12 and Week 26.

Missing values will be imputed 10,000 times. Completed datasets from the two parts detailed above will be combined into a single dataset. Each completed dataset will be analyzed using an analysis of covariance (ANCOVA) of the change in HbA1c from baseline to Week 26, including the fixed categorical effects of treatment group (SAR341402, NovoLog/NovoRapid), the randomization strata of geographical region and type of diabetes (Europe T1DM, US T1DM, US T2DM, Japan T1DM) and prior use of NovoLog/NovoRapid (Yes, No), as well as the continuous fixed covariate of baseline value. Results from the 10,000 analyses will be combined using Rubin's formula (MIANALYZE procedure in SAS).

Statistical Analysis Plan SAR314102-EFC15081 - insulin aspart 28-Feb-2018 Version number: 1

The adjusted least squares (LS) mean of the change in HbA1c from baseline to Week 26 for each treatment group (SAR341402, NovoLog/NovoRapid) will be estimated, as well as the between-group LS mean difference of SAR341402 versus NovoLog/NovoRapid, with the corresponding standard errors and 2-sided 95% CIs. These values will be calculated using the observed proportions of patients in the randomization strata and the observed baseline mean HbA1c in the ITT population.

Non-inferiority will be demonstrated if the upper bound of the 2-sided 95% CI of the difference between SAR341402 and NovoLog/NovoRapid on the ITT population is <0.3%.

Second step analysis:

If non-inferiority of SAR341402 over NovoLog/NovoRapid is demonstrated, using a hierarchical step-down testing procedure, the following additional analysis will be performed (not as primary objective): the inverse non-inferiority (of NovoLog/NovoRapid over SAR341402) will be tested looking at the lower bound of the 2-sided 95% CI of the difference between SAR341402 and NovoLog/NovoRapid in the ITT population. Non-inferiority of NovoLog/NovoRapid over SAR341402 will be demonstrated if the lower bound is >-0.3%.

If SAR341402 is shown to be non-inferior to NovoLog/NovoRapid and NovoLog/NovoRapid non-inferior to SAR341402, similar efficacy (equivalence) of SAR341402 and NovoLog/NovoRapid will be assumed.

2.4.4.1.2 Sensitivity analysis

Sensitivity analyses will be conducted to assess the robustness of primary efficacy analysis with regard to missing data (5).

Description of missing data

The following analyses will be performed on the ITT population to explore the missing data frequency and pattern:

- As described in Section 2.2, KM plots/estimates of the cumulative incidence of IMP discontinuation will be provided by treatment group for the main 6-month period, with hazard ratio and 95% CI estimated using Cox regression model.
- Availability of HbA1c at each visit will be provided by treatment group according to the status of the patient (discontinued treatment or not).
- The number and disposition of patients with missing data will be described according to the availability for the primary efficacy analysis (Consolidated Standards of Reporting Trials [CONSORT] diagram according to missing data pattern).

- In order to explore missing data patterns for HbA1c, number and percentage of patients in each of the following categories will be presented by treatment group and patient status at Week 26 (Patient without permanent treatment discontinuation, patient with permanent treatment discontinuation):
 - Pattern 1: patients without baseline if any,
 - Pattern 2: patients with baseline but without post-baseline value during the main 6-month randomized period,
 - Pattern 3: patients with baseline and at least one post-baseline value during the main 6-month randomized period but not at Week 26,
 - Pattern 4: patients with baseline and Week 26 value during the main 6-month randomized period.
- Baseline characteristics and HbA1c values by visit will be presented by missing data pattern for each treatment group, using descriptive statistics and/or graphs.

Return to baseline analysis

To assess the robustness of primary efficacy analysis with regard to the imputation of missing data, a sensitivity analysis will be performed using a multiple imputation method that models a "return-to-baseline" for patients having missing data at Week 26.

For each patient in the SAR341402 and NovoLog/NovoRapid group in the ITT population, the missing HbA1c values at Week 26 will be imputed as equal to the patient's baseline plus an error. The error will be normally distributed with mean zero and standard deviation set equal to the estimated pooled standard deviation. No negative value will be allowed (in this case, another value will be redrawn).

Missing HbA1c values will be imputed 10,000 times to generate 10,000 datasets with complete HbA1c values at Week 26. In each dataset, the change in HbA1c from baseline to Week 26 will be derived from observed and imputed HbA1c values at Week 26. Each completed dataset will be analyzed using an ANCOVA of change from baseline to Week 26 in HbA1c (%), including the fixed categorical effects of treatment group (SAR341402, NovoLog/NovoRapid), the randomization strata of geographical region and type of diabetes (Europe T1DM, US T1DM, US T2DM, Japan T1DM) and prior use of NovoLog/NovoRapid (Yes, No), as well as the continuous fixed covariate of baseline value. Results from the 10,000 analyses will be combined using Rubin's formula (MIANALYZE procedure in SAS).

The adjusted LS mean of the change in HbA1c from baseline to Week 26 for each treatment group (SAR341402, NovoLog/NovoRapid) will be estimated, as well as the between-group LS mean difference of SAR341402 versus NovoLog/NovoRapid, with the corresponding standard errors and 2-sided 95% CIs. These values will be calculated using the observed proportions of patients in the randomization strata and the observed baseline mean HbA1c in the ITT population.

Tipping point analysis

In order to assess the impact of missing data, a tipping-point analysis based on the pattern mixture model approach will be performed in the ITT population as described below.

The considered pattern mixture model will introduce a sensitivity parameter, δ , corresponding to the difference in mean change from baseline in HbA1c between patients with missing data and patients with observed data. Estimations will be performed using the multiple imputation approach "return-to-baseline" as described above. δ will be added to the imputed values in the SAR341402 group whereas the imputed values in the NovoLog/NovoRapid group will not change ($\delta = 0$ corresponding to the missing at random [MAR] assumption). For each value δ will correspond an estimated LS mean in HbA1c per group and an estimated treatment effect.

To investigate how the conclusions depend on the adopted values of δ , the testing will be repeated over a range of plausible values for δ , the treatment effect being penalized by a positive value and favored by a negative value. A specific illustration on the value of the minimum penalty leading to a non-rejection of the null hypothesis (upper limit of the 95% CI of treatment effect greater than 0.3%) will be provided (6).

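### The tipping-point analysis labels δ = 0 as missing at random, but δ is added to return-to-baseline values, so δ = 0 is the return-to-baseline analysis and δ is not the missing-versus-observed difference

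*SAP*

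**What the plan says.** Three statements in SAP 2.4.4.1.2, under the tipping-point analysis, concern δ.

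- Its meaning: "corresponding to the difference in mean change from baseline in HbA1c between patients with missing data and patients with observed data".
- Its mechanics: "Estimations will be performed using the multiple imputation approach", the approach named being return-to-baseline. δ "will be added to the imputed values in the SAR341402 group whereas the imputed values in the NovoLog/NovoRapid group will not change".
- Its zero point: δ = 0 is described as "corresponding to the missing at random [MAR] assumption".

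The sign rule is "the treatment effect being penalized by a positive value and favored by a negative value". The SAP promises to report the smallest penalty at which the upper 95% limit exceeds 0.3%.

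The return-to-baseline analysis is defined just before this, in the same section: "the missing HbA1c values at Week 26 will be imputed as equal to the patient's baseline plus an error". The error is normal with mean zero and the pooled SD, and both arms are treated alike.

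Protocol 11.4.2.1.2 only announces sensitivity analyses for missing data. SAP 1.6 records no statistical modification. Neither settles what δ means.

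**The concern.** The three statements cannot all hold unless the observed mean change happens to be zero, which the SAP does not assume. A missing-at-random imputation takes its centre from observed data, given covariates. Return-to-baseline takes its centre from the patient's own baseline, and neither Week 12 nor Week 26 data in other patients move it.

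The minimum penalty is the main number this analysis produces, and it is useful only if a reader can judge whether it is plausible. Someone told that zero means missing at random will read the penalty as a departure from observed patients. It is in fact a departure from no change since baseline. The mislabel could pass unchanged into table footnotes and the 6-month report.

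**Working it through.** **Inputs.** From SAP 1.3: 290 patients per arm, SD 1.0, margin 0.3. The documents give no expected HbA1c change and no missing-data rate, so those below are assumptions.

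**The plan's own figure.** SE = √(2/290) = 0.0830. Power = Φ(0.3/0.0830 − 1.96) = 95.08%, and for both directions 2 × 0.9508 − 1 = 90.16%. Both match the stated 95% and 90%. The SAP gives no numerical tipping-point result to reproduce.

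**What δ is.** Let y be the observed SAR341402 mean change. The imputed mean change is 0 + δ, so missing minus observed = δ − y. At δ = 0 this is −y, not 0. A simulation with 10% missing gave a gap of 0.30 for y = −0.3 and 0.20 for y = −0.2 under return-to-baseline, and 0.00 after rounding under a missing-at-random imputation.

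The SAP does not state the direction of the difference or whether the observed patients are those of one arm or both. The sign rule supports missing minus observed. Within-arm is assumed here.

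**Tipping values.** Let yT, yC be observed mean changes, mT, mC missing fractions, and a the imputed mean at δ = 0 (0 for return-to-baseline, y for an observed-data anchor).

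- Estimate = [(1−mT)yT + mT(aT+δ)] − [(1−mC)yC + mC·aC]
- Within variance W = (vT+vC)/290, with v = 1 + m(1−m)g², gT = aT+δ−yT, gC = aC−yC
- Between variance B = (mT+mC)/290 for return-to-baseline; for the observed-data anchor, the sum over arms of (n_mis + n_mis²/n_obs)/290²
- Solve estimate + 1.96·√(W+B) = 0.3

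Worked case, 8% missing and a change of −0.4 in both arms, return-to-baseline: δ = 1.503; estimate = 0.08 × 1.503 = 0.1202; vT = 1.2665; vC = 1.0118; W = 0.007856; B = 0.000552; SE = 0.0917; upper limit = 0.1202 + 1.96 × 0.0917 = 0.300. Missing minus observed = 1.503 + 0.4 = 1.903.

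Both arms −0.4, equal missingness:

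| Missing per arm | Reported δ | δ − y | Observed-data anchor |
|---|---|---|---|
| 5% | 2.38 | 2.78 | 2.44 |
| 8% | 1.50 | 1.90 | 1.54 |
| 12% | 1.00 | 1.40 | 1.02 |
| 15% | 0.79 | 1.19 | 0.80 |

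The first and last value columns differ by about 2 to 3% before rounding.

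Unbalanced cases:

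| Case | Reported δ | δ − y | Observed-data anchor |
|---|---|---|---|
| 8% each; SAR341402 −0.3, comparator −0.4 | 0.46 | 0.76 | 0.37 |
| 6% SAR341402, 12% comparator; both −0.4 | 2.30 | 2.70 | 2.01 |
| 12% SAR341402, 6% comparator; both −0.4 | 0.83 | 1.23 | 1.04 |

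The starting estimates explain the direction. In the first case return-to-baseline shrinks the observed difference from 0.10 to 0.92 × 0.10 = 0.092. With unequal missingness it starts from 0.94 × (−0.4) − 0.88 × (−0.4) = −0.024 in the second case and +0.024 in the third, against 0 for the observed-data anchor.

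A simulation of the 8% balanced case and the three unbalanced cases under both anchors (1,500 trials, 60 imputations) gave mean upper limits of 0.294 to 0.303 at the solved values, against the target of 0.300. Baseline covariates were ignored.

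**The case against.** The strongest reply is that little turns on this. The procedure can be run as written: the imputation method, the arm that receives δ, the sign and the tipping condition are all stated. A return-to-baseline anchor is a legitimate choice. Non-inferiority is decided by the primary analysis in SAP 2.4.4.1.1, and the tipping point has no pass or fail threshold. SAP 2.4 already plans observed-case changes by visit and arm, so a reader could subtract. All of that stands, and it makes this a correction of meaning rather than of method.

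A reader might infer from the δ − y columns that the SAP understates robustness by a large fraction, for example 1.50 against 1.90. The documents do not support that, for three reasons.

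- The 1.90 tips the result only because comparator patients with missing data have also been moved 0.4 from their observed peers. A reader who believed the missing-at-random label would be expecting the observed-data value, 1.54.
- The gap depends on an assumed fall in HbA1c. Patients enter already on aspart or lispro with a basal insulin (protocol 7.1) and usually convert unit for unit (8.1.5.1), so a change near zero is plausible, although titration to target could lower HbA1c. At zero change the gap vanishes.
- The sign is not fixed. With SAR341402 worse by 0.10, the reported 0.46 is above the observed-data value of 0.37, so there the label makes the result look more robust, not less.

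None of this removes the contradiction.

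**Conclusion.** The point holds as an error of definition. δ = 0 is the return-to-baseline analysis, and the reported penalty is the mean change from baseline assigned to SAR341402 patients with missing Week 26 data. Even if the observed mean change were zero, the means would agree but the imputation would still not condition on observed data as missing at random requires.

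On the within-arm reading, the offset equals the observed SAR341402 mean change: zero at no change, 0.1 to 0.6 for assumed falls of 0.1 to 0.6, and reversed if HbA1c rises. On a pooled reading the size differs, but the label is still wrong. Against an observed-data anchor, the tipping value differs by about 2 to 3% in the balanced cases at −0.4, and by more, in either direction, when the arms or missingness differ. No direction of bias should be claimed. The primary test, alpha and power do not depend on it.

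**What to change.** In SAP 2.4.4.1.2, before the 6-month database lock:

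1. Delete the missing-at-random label and state that δ = 0 is the return-to-baseline analysis.
2. Define δ as the mean change from baseline assigned to SAR341402 patients with missing Week 26 HbA1c, with comparator patients with missing data held at baseline.
3. Print the observed SAR341402 and comparator mean changes beside the tipping value, so that missing minus observed can be read off for each arm.

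The cost is one definition, one parenthesis and two figures already planned for reporting elsewhere.

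Adding δ to the primary two-part imputation instead is optional and a matter of preference. It would tie the tipping point to the primary result and reuse the 10,000 datasets. However, its first part rests on few observed discontinuers, as the SAP itself expects: "Due to the anticipated small number of these latter patients, a basic imputation model will be built". If that route is taken, δ should be defined as the shift from that imputation, with return-to-baseline kept as a separate analysis.

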2.4.4.1.3 Supportive analysis

In the case the per-protocol population will represent less than 95% of the ITT population, a supportive analysis will be conducted on the per-protocol population to evaluate the robustness of the conclusion of the primary efficacy analysis when excluding the patients that may increase the chance of reaching non inferiority conclusion.

Data in the per-protocol population will be analyzed using an ANCOVA of the change in HbA1c from baseline to Week 26, including the fixed categorical effects of treatment group (SAR341402, NovoLog/NovoRapid), the randomization strata of geographical region and type of diabetes (Europe T1DM, US T1DM, US T2DM, Japan T1DM) and prior use of NovoLog/NovoRapid (Yes, No), as well as the continuous fixed covariate of baseline value.

The adjusted LS mean of the change in HbA1c from baseline to Week 26 for each treatment group (SAR341402, NovoLog/NovoRapid) will be estimated, as well as the between-group LS mean difference of SAR341402 versus NovoLog/NovoRapid, with the corresponding standard errors and 2-sided 95% CIs. These values will be calculated using the observed proportions of patients in the randomization strata and the observed baseline mean HbA1c in the PP population.

2.4.4.1.4 Subgroup analyses

The primary efficacy endpoint will be further analyzed to examine whether the treatment effect varies in subgroups defined by the following baseline covariates:

- Race (American Indian or Alaska Native, Asian, Black or African American, Native Hawaiian or Other Pacific Islander, White, More than One Race, Unknown or Not Reported),
- Ethnicity (Hispanic or Latino, Not Hispanic or Latino, Unknown /Not Reported),
- Age group (<65, \geq 65 to <75, \geq 75 years of age),
- Sex (male, female),
- Baseline BMI ($<30, \geq 30 \text{ kg/m}^2$),
- Baseline estimated GFR categories (<60, ≥60 mL/min/1.73m²),
- Randomization stratum of type of diabetes (T1DM, T2DM),
- Randomization stratum of screening HbA1c (< 8.0%, $\geq 8.0\%$),
- Randomization stratum of prior use of NovoLog/NovoRapid (Yes, No),
- Type of comparator (NovoLog, NovoRapid),
- Regions (North America, Western Europe, Eastern Europe, ROW),
- Duration of diabetes ($<10, \ge 10$ years).

The treatment effect across the subgroups defined above will be estimated for the primary efficacy variable (change in HbA1c from baseline to Week 26) in the ITT population and separately for the T1DM patients, using all post baseline HbA1c data available during the main 6-month randomized period. The same multiple imputation approach as described for primary analysis will be applied, using the 10,000 completed datasets generated for the primary analysis. Each completed dataset will be analyzed using an ANCOVA of change from baseline to Week 26 in HbA1c, including the fixed categorical effects of treatment group (SAR341402, NovoLog/NovoRapid), the randomization stratum of prior use of NovoLog/NovoRapid (Yes, No), the corresponding subgroup factor and subgroup factor-by-treatment interaction, and the continuous fixed covariate of baseline value. The randomization strata of geographical region and type of diabetes (Europe T1DM, US T1DM, US T2DM, Japan T1DM) will not be included in the model. Results from the 10,000 analyses will be combined using Rubin's formula (MIANALYZE procedure in SAS).

When the subgroup considered is the randomization stratum of screening HbA1c ($<8.0, \ge8.0\%$), the baseline HbA1c value will be removed from the model.

When the subgroup considered is the randomization stratum of prior use of NovoLog/NovoRapid (Yes, No), the randomization stratum of prior use of NovoLog/NovoRapid (Yes, No) will be included only once in the model (as subgroup factor).

The adjusted LS mean of the change in HbA1c from baseline to Week 26 for each treatment group (SAR341402, NovoLog/NovoRapid) within each subgroup will be estimated, as well as the between-group LS mean difference of SAR341402 versus NovoLog/NovoRapid, with the corresponding standard errors and 2-sided 95% CIs. The significance level of the treatment-by-subgroup factor interaction will be provided for descriptive purpose. Forest plots will be provided.

Further subgroup analyses may be performed if deemed necessary for interpretation of results.

